9.6.1. Case Report Forms (CRFs)

As used in this protocol, the term CRF should be understood to refer to either a paper form or an electronic data record or both, depending on the data collection method used in this study.

A CRF is required and should be completed for each included patient. The completed original CRFs are the sole property of Pfizer and should not be made available in any form to third parties, except for authorised representatives of Pfizer or appropriate regulatory authorities, without written permission from Pfizer. The investigator shall ensure that the CRFs are securely stored at the study site in encrypted electronic and will be password protected to prevent access by unauthorized third parties.

The investigator has ultimate responsibility for the collection and reporting of all clinical, safety, and laboratory data entered on the CRFs and any other data collection forms (source documents) and ensuring that they are accurate, authentic/original, attributable, complete, consistent, legible, timely (contemporaneous), enduring, and available when required. The CRFs must be signed by the investigator or by an authorized staff member to attest that the data contained on the CRFs are true. Any corrections to entries made in the CRFs or source documents must be dated, initialed, and explained (if necessary) and should not obscure the original entry.

The source documents are the hospital's or the physician's chart. In these cases, data collected on the CRFs must match those charts.

9.6.2. Record Retention

To enable evaluations and/or inspections/audits from regulatory authorities or Pfizer, the investigator agrees to keep records, including the identity of all participating patients (sufficient information to link records, eg, CRFs and hospital records), original signed informed consent/assent documents (if applicable), copies of all CRFs, safety reporting forms, source documents, detailed records of treatment disposition, and adequate documentation of relevant correspondence (eg, letters, meeting minutes, and telephone call reports). The records should be retained by the investigator according to local regulations or as specified in the clinical study agreement (CSA), whichever is longer. The investigator must ensure that the records continue to be stored securely for so long as they are retained.

If the investigator becomes unable for any reason to continue to retain study records for the required period (eg, retirement, relocation), Pfizer should be prospectively notified. The study records must be transferred to a designee acceptable to Pfizer, such as another investigator, another institution, or to an independent third party arranged by Pfizer.

Study records must be kept for a minimum of 15 years after completion or discontinuation of the study, unless ARW and Pfizer have expressly agreed to a different period of retention via a separate written agreement. Record must be retained for longer than 15 years or as required by applicable local regulations.

The investigator must obtain Pfizer's written permission before disposing of any records, even if retention requirements have been met.

9.7. Data Analysis

Detailed methodology for summary and statistical analyses of data collected in this study will be documented in a SAP, which will be dated, filed and maintained by the sponsor. The SAP may modify the plans outlined in the protocol; any major modifications of primary endpoint definitions or their analyses would be reflected in a protocol amendment.

All analyses will be conducted using Stata 17 software, version 17 or the latest available version (StataCorp, College Station, Texas).

The study is not intended to test hypotheses and is primarily descriptive in nature. Frequencies and percentages will be reported for categorical variables, including the percentage of missing/unknown data, while counts, number of missing, means, medians, SDs, SEs, first and third quartiles, minimum and maximum values will be reported for continuous numeric variables. Where applicable, all estimates will be described with accompanying 95% CIs. Time to event analyses will be conducted, with KM curves and 95% CI estimated for KM curves outputted. Finally, Sankey diagrams will be generated to aid in interpretation of the analysis of treatment patterns.

Where missing values are found in a particular variable, these will be reported either as an unknown categorical group or as the number of patients with a missing data point for continuous variables. In cases where there are large amounts of missing data or where the volume of missing data is differential between important clinical/prognostic groups, imputation may be used and reported in a sensitivity analysis with appropriate methods of imputation decided at analysis phase with the lead study analyst. The threshold of missing data which will require imputation and sensitivity analyses will be determined following initial review of the data.

Data analysis will be aligned with data extracted/collected from all data sets. Where specific variables or outcomes cannot be assessed/described subgroup analyses could be conducted for a subset of patients from certain data sources. Details of potential bias in this dataset are detailed in [Section 9.9](#).

In the event of a data source being unable to provide data for ARW led analysis, variables and outcomes will be assessed using aggregated outputs.

9.8. Quality Control

For chart review:

Data from the eCRF will be stored in the study database. The database will be housed and managed by ARW during the study and analysis. Any data transfers to Pfizer will be carried out via a Secure File Transfer Protocol (SFTP) to ensure any international transfers are safeguarded. ARW's data server is based within the UK. Following completion of the study, the study database will be archived and subsequently permanently deleted, in accordance with ARW's and Pfizer's Master Services Agreement.

Version control will be used during the development of all data collection materials to ensure there is an auditable record of requested updates and changes is available.

For the chart review data collection in Austria and Belgium, each individual eCRF will be reviewed by 2 members of the project team to check for logical and medical consistency. Queries will be raised throughout the data management process and will only be closed following the satisfactory correction or explanation by each site. All queries will be logged within the EDC as part of the audit trail and will also be recorded within the data management plan. Following the review and sign-off of each eCRF by 2 members of the project team, the eCRF will be locked and will not be accessible for further data entry or changes. In Germany, where patient data must be completely anonymised (ie, no linkage document is permitted), all entered data will be reviewed, but data queries will be limited by the inability for sites to reidentify patients. As automated checks will be programmed into the eCRF, the impact on the completeness of the data in Germany is expected to be minimal.

When all checks have been completed to the satisfaction of the project manager, the database will be considered complete and the database will be locked. This formally announces that there is no intention to make any further changes to the data and that data analysis can proceed. A database lock declaration form will be completed by the project manager and the form will be kept in the study file. The locked database will be saved into a folder with restricted access. A copy of the locked database will be made available to the analyst.

Secondary data analysis:

For quality control purposes, documented evidence of correct interpretation of the study protocol will be achieved through development of a detailed SAP, reviewed, and approved by the Pfizer study team, and an extensive decision log maintained and updated by the ARW study team, which can be shared with Pfizer throughout the course of the study. Documented evidence of correct execution of the study protocol will be achieved through completion of ARW's internal quality control (QC) checklist (see [ARW QC Checklist](#)) by both the project analyst and an independent QC analyst, which, on completion, can be made available to the Pfizer study team on request. The independent QC analyst will be responsible for a detailed review of the project analyst's programming code and outputs prior to sign-off, ie, no code replication.

On production of study results, ARW will perform QC of the outputs including, but not limited to, logic checks on base sizes, missing values and totals, consistency of output across tables, extreme/unexpected values and results, typographical errors and interpretations (where applicable). Any issues identified during this process will be logged and resolved to completion with the appropriate analyst team. On receipt of any updated output, additional checks will be performed in accordance with the initial data check to ensure all issues have been adequately resolved and no further issues are identified. In the event that the original issues have not been resolved or further issues have been identified, the quality control process will be repeated.

9.9. Limitations of the Research Methods

Study design limitations:

- The overall sample size of patients (~230) may limit comparisons if subgroup numbers are low, such as ELN risk status (intermediate and favourable) and cytogenetic risk subgroups. However, the sample size is not substantially low in relation to the global population of interest. Furthermore, this is purely a descriptive study with no statistical comparisons and so the assessment of treatment patterns and effectiveness outcomes will not be affected by the small sample sizes.
- As this a multi-county multisource study, it is likely that there will differences in data variable availability. To mitigate this, the eCRF used for Austrian, Belgian, and German sites will be designed using knowledge of datasets known to collect data from medical records. When requesting data from the Austrian Myeloid Registry, variables will be requested in this same format where possible. Furthermore, during analysis where specific variables or outcomes cannot be assessed/described in one data source, subgroup analyses could be conducted for a subset of patients from certain data sources.
- GO-based treatment regimens and dosing schedules may differ through the different countries, adding to the complexity of the assessment of effectiveness outcomes. Subgroup analyses could be conducted for subsets of patients receiving the same or similar treatment regimens and or dosage schedules. Furthermore, dosing information per regimen may not be available in the data sources. For example, a total dose of GO may be provided, without numbers and/or timings. Nevertheless, number of doses is likely to be imputable due to prescribing guidelines and consistent quantities of GO supplied in vials (each dose). Timings of doses could be derived algorithmically, details of which would be provided in the SAP.
- The multiple cytogenetic risk groups included in the study cohorts, could similarly add complexity to the assessment of effectiveness outcomes. As a result, the analyses could include a stratification of risk group, subject to sample sizes.

- The minimum follow-up period has been set to 3 months. Consequently, for a large number of patients, OS and EFS maybe not assessable. These patients will be censored for such analyses.

Data source related limitations:

- For the chart review, selection bias may arise. Site participation is influenced by willingness to take part, and may be based on workload, levels of consulting patients during the data collection period, or familiarity with the research nature of the study. It should also be noted that the sites eligible for inclusion in the study are those with whom Pfizer have existing relationships with, and those ultimately selected for inclusion may be those deemed most suitable based on the feasibility assessment stage (ie, those sites with higher numbers of patients or who are most suited to executed non-interventional data collection studies) may be chosen over those considered to be less suitable. These factors introduce a bias whereby patients from non-participating sites are not represented in the results. Nonetheless, this method of site selection is the most practical approach for a non-interventional study such as this, whereby resources and timelines, to an extent, dictate the sites that can be considered eligible for inclusion.
- Further to the previous point, in the event that informed consent is required for patient participation, the patient sample may potentially be biased towards less severe patients who are capable and willing to provide consent to participate. To mitigate both of these selection biases, patient demographic and clinical characteristic data will be captured to allow for comparisons with published datasets to understand the generalizability of results. Additionally, should informed consent be required in Austria and/or Belgium and/or Germany, a legally acceptable representative would be permitted to provide informed consent on behalf of the patient should they be unable to consent, reducing the bias associated with the need to obtain patient consent. Based on initial information, informed consent is unlikely to be necessary to process pseudoanonymised data in Austria and Belgium, and is not required in Germany to process completely anonymised data. In order to avoid this limitation, efforts will be made to ensure a waiver for informed consent is provided by local IRBs.

- Missing data from the eCRF is an important limitation to consider in this study. Some variables that we intend to collect may not be present within a patient's medical record and so cannot be extracted during the eCRF. To address this limitation, the standardised eCRF will undergo a thorough review process prior to implementation which will help ensure that the content is appropriate for the listed research objectives and can reasonably be expected to be captured within patients' medical notes. Further, the eCRF will be designed in such a way that incomplete variables will be flagged and eCRFs will not be able to be locked until all variables have been completed. Where data is not available in Austria and Belgium, the sites will be asked to provide an explanation for the missing data, thus providing the opportunity to capture data not provided during initial data entry. In Germany, it is important to note the additional limitation that data will need to be completely anonymised, meaning a patient linkage file cannot be created and thus, it will not be possible to query patient data that requires identification through a linkage document.
- Secondary data often poses a limitation in regard to data lag. The Austrian Myeloid Registry may not have data for patients available to the present day – the data lag associated with this registry; however, is currently unknown but will be determined through custodian contact.
- Data access to registries is often complex, due to the application requirements, ethical approval processes and policies behind transfer of data; these complexities often cause long timelines receipt of aggregated data. ARW and Pfizer are currently in communication with data custodians to understand the feasibility of accessing the registry and ways of accessing registry data. If registry access is required, ARW will conduct the necessary processes to allow for efficient data access.
- The Austrian Myeloid Registry had reduced data collection in recent years due to the COVID-19 pandemic. Consequently, the current number of patients treated with GO with data available in the registry is relatively low. Nonetheless, data collection should increase in the coming months enabling more GO-treated patient data. The timeline for data collection should align with eCRF-based data collection for the Austrian, Belgian and German sites, as a result, data extraction and analysis should align with the both the registry and site-collected data.
- It is currently unknown whether de novo status will be explicitly indicated within the Austrian registry, this will be confirmed up contact with data custodians. It is likely that patients will enter the registry upon de novo diagnosis however. If de novo status is not explicitly captured, other variables/information will be considered to determine this. Furthermore, GO-based treatment regimens are expected to be used on only de novo patients.

- Information regarding MRD status may be missing across data sources. Current knowledge suggests that is captured in the Austrian Myeloid Registry. This may be seen in Austrian, Belgian, and German sites also. When MRD status is captured, it could be described for the relevant patients within a subgroup analysis.

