9. RESEARCH METHODS

9.1. Study Design

All assessments described in this protocol are performed as part of normal clinical practice or standard practice guidelines for the patient population and healthcare provider specialty in the countries where this non-interventional study is being conducted.

The following study has been designed to address the limited knowledge of real-world treatment patterns and effectiveness outcomes of GO treatment in AML, according to recent licensed dosing. As a result of the rarity of disease and limited patient numbers, a multi-country study has been designed, in order to gain sufficient sample size and also to assess the differences of treatment patterns in different countries. Data from the following countries will be sought:

- Austria
- Belgium
- Germany

All countries and data sources specified within the protocol are provisional and subject to final feasibility confirmation. The current selection of data sources is described below and in [Section 9.4](#). They have been selected due to their associated sufficiently sized GO patient population and data availability, which was identified through previous feasibility work.

A combination study design approach of a retrospective cohort study and retrospective chart review will be employed to address the study objectives described in [Section 8](#). The cohort study will be conducted using a disease-specific dataset in Austria. This source was identified during a previous feasibility assessment as a dataset with the required data variables. The chart review will be conducted across various sites in Austria, Belgium, and Germany. Belgium and Germany have a high patient population, but no appropriate dataset was identified, hence the combination approach. The Austrian site and dataset together, in addition to the site-reported data captured in Belgium and Germany will provide a substantial sample size to address the research objectives – see [Section 9.2](#) for a detailed explanation of each data source.

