The Austrian Myeloid Registry aims to assess the treatment patterns, clinical outcomes and quality of life of patients with myeloid diseases from 15 Austrian sites.¹⁵ Data will be extracted for patients who meet the eligibility criteria outlined in [Section 9.2.1](#) and [9.2.2](#), resulting in an estimated 30 patients. The data to be abstracted or extracted will include but is not limited to baseline demographics and clinical characteristics, treatment patterns and effectiveness outcomes. Where required, treatment patterns and effectiveness outcomes will be defined using numerical and statistical methods. Initial feasibility investigations showed the registry extract data in a similar way to an eCRF and extract data from EMRs at multiple sites across Austria.

It is estimated that around 230 patients will be included across Austria, Belgium, and Germany; this comprises of 1 site plus 1 registry in Austria, 3 sites in Belgium and 1 site in Germany. However, the final number will vary from this estimate and that is permissible.

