9.5. Study Size

This study is purely descriptive and there will be no limit on the sample size in terms of patients meeting the eligibility criteria in [Section 9.2.1](#) and [9.2.2](#). Estimated sample sizes are presented below by county in Table 1. Sample sizes will be maximized where feasible and appropriate and will likely vary from the below estimates.

Table 1. Sample Size Estimations per Data Source

	Site name	Number of patients treated with GO
Austria	Medical University of Vienna	50
	Austrian Myeloid Registry	30
Belgium	UZ Leuven	50
	Az Sint Jan Brugge	42
	UZ Brussels	18
Germany	University of Cologne	40

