9.2.1 Exposure? (eg, date of dispensing, drug quantity, dose, number of days of supply prescription, daily dosage, prescriber)				
9.2.2 Outcomes? (eg, date of occurrence, multiple event, severity measures related to event)				
9.2.3 Covariates and other characteristics? (eg, age, sex, clinical and drug use history, co-morbidity, co-medications, lifestyle)				
9.3 Is a coding system described for:				
9.3.1 Exposure? (eg, WHO Drug Dictionary, Anatomical Therapeutic Chemical (ATC) Classification System)				
9.3.2 Outcomes? (eg, International Classification of Diseases (ICD), Medical Dictionary for Regulatory Activities (MedDRA))				
9.3.3 Covariates and other characteristics?				
9.4 Is a linkage method between data sources described? (eg, based on a unique identifier or other)				

PFIZER CONFIDENTIAL

Comments:

Exposure, outcomes, covariates, and other characteristics are described in **Section 8.3** of the protocol. This section captures the variables which will be captured/defined through the data provided by the sites submitted via the CRF and secondary data sources. The protocol itself does not indicate the exact variables which will be provided by the data sources themselves. These will be described in detail within the study Statistical Analysis Plan (SAP).

The coding system for any exposures, outcomes or covariates is not applicable to the secondary data source or the sites where a chart review will be used for data collection. There is no linkage that will be utilised.

Section 10: Analysis plan	Yes	No	N/A	Section Number
10.1 Are the statistical methods and the reason for their choice described?				8.7
10.2 Is study size and/or statistical precision estimated?				8.5

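### Section 9.9 says small samples will not affect the assessment because the study is descriptive; that is incorrect, and at the planned country sizes only large country differences can be told apart from sampling error

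*Protocol*

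**What the plan says.** The first bullet of Section 9.9 (Limitations of the Research Methods) begins by accepting that about 230 patients may limit comparisons when subgroups are small. It then says that the study is purely descriptive, without statistical comparisons, and concludes that "the assessment of treatment patterns and effectiveness outcomes will not be affected by the small sample sizes".

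Other sections bear on this:

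- Section 9.1 (Study Design) gives the reason for a multi-country study: "in order to gain sufficient sample size and also to assess the differences of treatment patterns in different countries".
- Section 9.5 (Study Size) says "Estimated sample sizes are presented below by county in Table 1". The table lists one expected count per source and no expected precision.
- Section 9.4 (Data Sources) gives the total: "It is estimated that around 230 patients will be included across Austria, Belgium, and Germany".
- Section 9.7 (Data Analysis) plans no hypothesis tests, but does plan 95% confidence intervals on estimates where applicable and on the Kaplan-Meier curves.

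**The concern.** In a descriptive study the sample size sets the precision of every percentage, median and survival estimate. Without a hypothesis test there is no power calculation to make, but the sampling error remains. The sentence therefore credits the design with a property it does not have, and it covers both the co-primary treatment patterns and the secondary effectiveness outcomes.

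It also conflicts with the rest of the protocol. If size had no effect on the assessment, seeking a sufficient sample across several countries (Section 9.1) would serve no purpose. And assessing how treatment patterns differ between countries is a comparison, even if no p-value is attached.

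What is at stake is interpretation. The limitations section tells readers how far to trust the results, and Section 12 foresees publication. A reader who takes the sentence at face value could report a gap of around 15 points in a dosing pattern, seen against 40 patients at one German site, as a country difference when chance alone could produce it.

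**Working it through.** **Inputs from the protocol.** Table 1 in Section 9.5:

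- Austria: Medical University of Vienna 50 and the Austrian Myeloid Registry 30 (Section 9.4 agrees on the registry: "resulting in an estimated 30 patients"), so 50 + 30 = 80.
- Belgium: UZ Leuven 50, Az Sint Jan Brugge 42 and UZ Brussels 18, so 50 + 42 + 18 = 110.
- Germany: University of Cologne 40.

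The total is 80 + 110 + 40 = 230, which reproduces the stated figure. The confidence level, 95%, is from Section 9.7.

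**Assumptions.** The protocol gives no expected proportion for any treatment-pattern variable, so two values are shown: 50%, where the interval is widest, and 80%. Patients are treated as independent (no clustering within sites) and no data are missing.

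**Step 1: one proportion.** Half-width = 1.96 × √(p(1−p)/n). For Germany at 50%: 1.96 × √(0.25/40) = 1.96 × 0.0791 = 0.155.

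| Group | n | p = 50% | p = 80% |
|---|---|---|---|
| All | 230 | 6.5 points | 5.2 points |
| Belgium | 110 | 9.3 | 7.5 |
| Austria | 80 | 11.0 | 8.8 |
| Germany | 40 | 15.5 | 12.4 |

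Exact intervals give a similar picture. For 50% of 40 the Clopper-Pearson interval is 33.8% to 66.2%, and for 50% of 230 it is 43.4% to 56.6%.

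**Step 2: difference between two countries.** Half-width = 1.96 × √(p(1−p)(1/n₁ + 1/n₂)). For Belgium-Germany at 50%: 1.96 × √(0.25 × (1/110 + 1/40)) = 1.96 × 0.0923 = 0.181.

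| Contrast | p = 50% | p = 80% |
|---|---|---|
| Austria-Belgium | 14.4 points | 11.5 points |
| Belgium-Germany | 18.1 | 14.5 |
| Austria-Germany | 19.0 | 15.2 |

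**Step 3: what size of true difference would show.** The Step 2 half-widths apply to an observed difference. The chance that the 95% interval excludes zero, for a given true difference, is:

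| True proportions | Austria-Belgium | Belgium-Germany | Austria-Germany |
|---|---|---|---|
| 50% vs 40% | 28% | 19% | 18% |
| 50% vs 30% | 80% | 59% | 55% |
| 50% vs 20% | 99% | 94% | 91% |

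A true difference of 10 points would usually be missed, and one of 30 points would usually be seen. At 20 points the result depends on whether Germany is one of the two countries.

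**The case against.** Much can be said for the protocol. The same bullet concedes that small subgroups may limit comparisons, and Section 9.9 makes stratification by risk group subject to sample size. Section 9.3 plans one combined multi-country dataset, for which a worst-case half-width of 6.5 points is reasonable. Section 9.7 already requires 95% intervals where applicable, so imprecision would largely be visible in the report. These points stand, and they keep the matter small. They do not rescue the sentence: the concession covers comparisons only, not the precision of a single estimate, and the conclusion that follows takes it back.

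One could also argue that sites enter every eligible patient, so there is no sampling error. The protocol does not take that view. It plans confidence intervals, and Section 9.2 wants the sample to represent the wider population treated with the drug.

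Some stronger readings are not supported:

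- **That the intervals are too wide for the study's purpose.** The protocol sets no target precision and no country difference of interest, so there is nothing to be too wide for.
- **That observed country differences of 15 to 20 points are all within sampling error.** At 50%, a 20-point difference exceeds all three half-widths, and a 15-point difference exceeds the one for Austria-Belgium.
- **That Annex 2 item 10.2 is wrongly ticked.** It asks "Is study size and/or statistical precision estimated". Section 9.5 estimates study size, so the answer is correct as worded.
- **That survival by country, or results for a single small site, will be unreliable.** The aim in Section 9.1 concerns treatment patterns. No survival analysis by country and no separate result for the smallest site is planned.

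**Conclusion.** The statement in Section 9.9 is incorrect and should go. Small numbers do affect the assessment: modestly for the pooled cohort (6.5 points at worst), more for single countries (9.3 to 15.5 points at 50%), and most for the country differences that Section 9.1 sets out to assess (14.4 to 19.0 points at 50%, 11.5 to 15.2 at 80%). At 50%, an observed difference must reach roughly 15 points for Austria-Belgium, or 18 to 19 points against Germany, before it can be told apart from sampling error.

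These figures rest on the Table 1 counts being met, on proportions of 50% or 80% chosen for illustration, and on independent patients with complete data. Clustering within sites or missing data would typically widen the intervals. The error lies in how precision is described; it does not invalidate any planned analysis.

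**What to change.** In Section 9.9, delete the sentence. In Sections 9.5 and 9.9, state the expected 95% half-widths for a proportion, overall and by country, and for the three country differences, with the assumed proportions and the assumption of no clustering or missing data. Add that pooled estimates are expected to be reasonably precise, that country differences are to be read with their 95% intervals, and that only large ones (at a proportion of 50%, roughly 15 points or more for Austria-Belgium and 18 to 19 or more against Germany) can be separated from sampling error.

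The cost is a few lines of text. No new data and no change to the design or the planned analyses are needed.
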